### ***Experimental protocol***

At the beginning of the baseline testing session, the researcher measures participants' weight and height using a scale and stadiometer; the body mass index will be calculated using REDCap programmed formula. Then the researcher will survey prosthetic embodiment by asking participants to fill out the revised version of the Trinity Amputation and Prosthesis Experience Scales (TAPES-R) and Prosthesis Embodiment Scale for Lower Limb Amputees (PEmbS-LLA), which are brief self-administered questionnaires to assess the adjustment and interaction of people with amputation to their prosthesis. Then, the researcher will ask participants to sit on a chair within parallel bars and remove their prosthesis. The researcher will examine the residual limb and places paper skin markers on specific landmarks over their residual limb (i.e. middle of the patella, tibial tuberosity, the distal end of the residual limb). Then, participants will stand securely inside parallel bars while the researcher captures the shape of their residual limb using a 3D scanner (OMEGA Scanner 3D, Willow Wood, Ohio, USA). The morphologic characteristics of the residual limb (i.e. length, circumference, and volume) will be recorded. If the participant finds it difficult to stand without the prosthesis, the scan will be performed in sitting and note in the assessment. The participant will then return to the sitting position and placement for the electromyography (EMG) electrodes (Trigno, Delsys Inc., Massachusetts, USA) will be determined on both the intact and amputated limbs based on the standard electrode placement guideline. However, for the amputated side, since the length of the muscles has changed, the location of the EMG electrodes needs to be determined specifically for each participant based on the new muscle bulk and optimal electrical signal activity. Electromyography of the tibialis anterior, medial and lateral heads of the gastrocnemius muscle will be recorded for both sides. Electrode locations will be marked and photographed to ensure consistency with subsequent testing session recordings. The skin will be cleaned using an alcohol pad and electrodes will be attached using paper tape.

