#### ***Data analysis and statistics***

Different levels of comparisons will be done to explore the impact of the targeted phantom motor execution program on phantom phenomena and physical function of people with TTA. Before starting analyses, the normality of distribution of the quantitative variables will be assessed by the Shapiro-Wilk test. Since there are two groups of participants, whether participants are matched on their demographic and clinical characteristics will be explored using independent t-test and chi-square statistics. Based on our expectation of normality of distribution for the quantitative variables, if it is the case, parametric statistical tests will be used. An independent t-test will be used to compare quantitative variables within-subjects for the amputated and non-amputated sides. Similarly, Mann-Whitney test and Chi square test will be used respectively to compare ordinal and nominal categorical variables within-subjects for the amputated and non-amputated sides. An independent t-test will be analyzed to compare quantitative variables between the two groups. Similarly, Mann-Whitney test and Chi square test will be used respectively to compare ordinal and nominal categorical variables between the two groups.

Two-way analysis of variance can be used to compare the simultaneous effect of groups assignment and prosthesis embodiment on PLC. Similarly, Friedman's two-way analysis of variance will be used to compare the simultaneous effect of group assignment and surgical closure on PLC.

Spearman's correlation coefficients will be calculated to explore the potential relationship of phantom phenomena responses with participants' characteristics (i.e. age, weight, height, body mass index, length of the residual limb, the circumference of the residual limb, time after amputation, and years of prosthesis use). Moreover, the potential relationship of the phantom phenomena responses with participants' gender, type of surgery, and footedness will be explored by point-biserial correlation assessment. The potential

relationship of the phantom phenomena responses with participants' prosthesis type will be explored by partial eta square correlation assessment.

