The linear regression analysis will be used to predict the effect of predictors / independent variables (i.e. clinical and demographic characteristics, and participants group) on outcomes / dependant variables (i.e. participants' physical function variables). Logistic regression analysis will be used to predict model of phantom phenomena based on participants' clinical and demographic characteristics, participants' group and physical function measures. Prior to regression analysis, regression assumptions including the normality, linearity, homoscedasticity (i.e. having equal variances in residuals of the predictors), and absence of multicollinearity (i.e. strong linear correlation between predictors as indicated by the average of the variance inflation factor (VIF) greater than 1) will be checked. For all statistical analyses, a p-value less than 0.05 will be considered statistically significant. The effect size and confidence intervals will be reported alongside other results to provide better judgment for the potential effects. All data will be analyzed offline using IBM SPSS software (Version 22.0, IBM Corp, New York, USA).

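### The multicollinearity cut-off, an average VIF above 1, sits at the lowest value a VIF can take, so in practice it flags trivial and severe collinearity alike

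*Combined protocol and SAP*

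**What the plan says.** The regressions are described at the end of *Data analysis and statistics*. The linear model takes as predictors the "clinical and demographic characteristics, and participants group", with physical function variables as outcomes. For the second model, "Logistic regression analysis will be used to predict model of phantom phenomena", using "participants' clinical and demographic characteristics, participants' group and physical function measures". Both therefore have several predictors.

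The assumption checks come first: "Prior to regression analysis, regression assumptions including the normality, linearity, homoscedasticity" and absence of multicollinearity. The last is described as "strong linear correlation between predictors as indicated by the average of the variance inflation factor (VIF) greater than 1".

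This is the only operational criterion for collinearity in the document. There is no tolerance, condition index or limit on individual predictors, and nothing says what is done when the criterion is met.

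**The concern.** A cut-off is useful only if some realistic models pass it and others fail. The value 1 is the floor of the VIF scale, reached only when a predictor has exactly zero linear association with the others in the sample. A rule that calls anything above that floor strong correlation gives the same answer for harmless and for severe collinearity.

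What is at stake is modest but real. The plan commits to checking this assumption before regression. Read literally, practically every model fails. If the rule is then set aside, whether collinearity is a problem will be judged after the data are seen, with no written standard.

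The case is not far-fetched. The participant characteristics listed for the correlation analysis include "age, weight, height, body mass index, length of the residual limb", and under *Experimental protocol* "the body mass index will be calculated using REDCap programmed formula" in the same sentence that has weight and height measured. The plan does not say that all three enter a regression. If they did, collinearity would be severe, and the written rule could not tell that model from a harmless one.

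**Working it through.** **Inputs.** From the plan: the criterion (average VIF > 1) and the fact that both models have several predictors. Sample size n and number of predictors k are not given in the supplied text, so every n and k below is an assumption. The cut-off is a rule and not a derived figure, so there is no plan calculation to reproduce.

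**Step 1: the lower bound.** VIF_j = 1/(1 − R_j²), where R_j² comes from regressing predictor j on the other predictors. Since 0 ≤ R_j² < 1, each VIF is at least 1, and so is their average. The average equals 1 only if all predictors are exactly uncorrelated in the sample. This step needs no assumed n or k.

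**Step 2: two predictors.** Here VIF = 1/(1 − r²), and both predictors share it.

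| r | VIF | Plan's label |
|---|---|---|
| 0.05 | 1/(1 − 0.0025) = 1.0025 | strong |
| 0.30 | 1/(1 − 0.09) = 1.099 | strong |
| 0.50 | 1/(1 − 0.25) = 1.333 | strong |
| 0.90 | 1/(1 − 0.81) = 5.26 | strong |
| 0.95 | 1/(1 − 0.9025) = 10.26 | strong |

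**Step 3: truly independent predictors.** For independent normal predictors with n > k + 2, the expected VIF is (n − 3)/(n − k − 2). With k = 2, n = 100 it is 97/96 = 1.010; with k = 9, n = 20 it is 17/9 = 1.889. In simulations with k = 2, 5 and 9 and n from 20 to 1000 (5,000 datasets each), the average exceeded 1 in 100% of datasets in every setting.

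**Step 4: the exception.** Two categorical predictors alone can be exactly uncorrelated. For two balanced binary variables and n = 20, the probability is C(10,5)²/C(20,10) = 63,504/184,756 = 0.34. Once a continuous covariate such as age is in the model, this does not happen in practice.

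**Step 5: why a higher limit on the average is not the answer.** Take nine predictors, one pair correlated 0.95 and the rest independent. The population VIFs are 10.26 for the pair and 1 for the other seven, so the average is (2 × 10.26 + 7)/9 = 3.06. Simulation with 10,000 datasets per n:

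| n | Average > 1 | Average > 5 | Any VIF > 5 | Any VIF > 10 |
|---|---|---|---|---|
| 20 | 100% | 60% | 99.7% | 90% |
| 40 | 100% | 17% | 99.9% | 80% |
| 100 | 100% | 0.5% | 100% | 72% |

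With nine independent predictors, a per-predictor limit of 5 flagged about 3% of datasets at n = 20 and none at n = 40 or 100; a limit of 10 flagged about 0.1% at n = 20 and none at the larger sizes. The plan's rule flagged 100% throughout.

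**Step 6: nominal predictors.** For a factor with more than two levels, the VIF of a dummy variable depends on the reference category. Assume 40 participants split 1, 19 and 20 over three levels. With the single participant as reference, the two dummies have r² = 0.475/0.525 = 0.905 (r about −0.95) and VIF = 1/(1 − 0.905) = 10.5. With the level of 20 as reference, r² = (0.025 × 0.475)/(0.975 × 0.525) = 0.023 and VIF = 1.02. The data are the same and only the coding differs, so a raw per-dummy limit could flag a harmless factor.

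**The case against.** The strongest reply is that nothing depends on the flag. The plan says only that assumptions will be checked. It has no rule for removing, combining or choosing predictors, and an analyst who computes the VIFs will still see whether they are near 1 or near 100. What fails is the written label, not an estimate, p-value or confidence interval. This stands, and it is why the point is minor.

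It can also be said that the word strong, or an unstated intention of substantially above 1, saves the rule. It does not. Strong correlation is said to be indicated by the average exceeding 1, and no other number is offered.

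Three stronger readings are tempting and are not supported:

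- A reader might infer that no model could ever meet the assumption. Step 4 shows an exception for purely categorical predictors, so the claim is limited to models with several predictors, at least one continuous.
- A reader might infer that predictors would be wrongly dropped or the regressions abandoned. The document attaches no such consequence to the check.
- A reader might infer that the comparison of the randomised groups is compromised. For that the plan states separately, "An independent t-test will be analyzed to compare quantitative variables between the two groups", with other tests for categorical variables, and none of these uses the VIF.

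**Conclusion.** Wrong as written; minor. The stated threshold is the minimum of the VIF scale, so for realistic models the check cannot separate trivial from severe collinearity, and the assumption as worded cannot realistically be met. This follows from the definition of the VIF and does not rest on any assumed sample size. The simulated percentages do rest on assumed n, k and correlations, and serve only to compare possible replacements. The effect is limited to the multicollinearity check for the linear and logistic regressions.

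**What to change.** In *Data analysis and statistics*, replace the cut-off with a pre-specified limit on each predictor's own VIF, clearly above 1. Limits of 5 or 10 are conventional; the documents do not favour either. For any nominal predictor with more than two levels (prosthesis type may be one; its levels are not given), use the generalised VIF, adjusted for its degrees of freedom, so that the result does not depend on the reference category.

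Then state what follows if the limit is exceeded. One option is to keep the group term always, and to drop or combine the flagged covariate that is lowest in an order written before the data are seen.

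One caution applies. It would be natural to add that the check is blind to results because VIFs are computed from predictors only. That is safe only for models whose predictors are all measured at baseline. The logistic model includes physical function measures, which are trial outcomes assessed again after the three-week programme, and the plan does not say which values enter. Such a reassurance should be left out or limited to models with baseline predictors.

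The cost is a sentence or two of text and the choice of a conventional limit. No new data and no change to trial conduct are needed.
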